15.2 Methods and Timing for Assessing, Recording, and Analyzing Safety Parameters

15.2.1 Adverse Events

Adverse Event (AE):

International Conference on Harmonisation (ICH) E6 defines an AE as any untoward medical occurrence in a patient or clinical investigation subject administered a pharmaceutical product regardless of its causal relationship to the study treatment. An AE can therefore be any unfavorable and unintended sign (including an abnormal laboratory finding), symptom, or disease temporally associated with the use of a medicinal (investigational) product. The occurrence of an AE may come to the attention of study personnel during study visits and interviews of a study treatment recipient presenting for medical care, or upon review by a study monitor.

All AEs, including local and systemic reactions, not meeting the protocol-defined criteria for serious adverse events (SAEs) should be captured on the appropriate data collection form and eCRF. Information to be collected for unsolicited AEs includes event description, date of onset, study clinician's assessment of severity and relationship to study product and alternate etiology (if not related to study product) (assessed only by those with the training and authority to make a diagnosis), date of resolution/stabilization of the event, seriousness and outcome. All AEs occurring while on study will be documented appropriately regardless of relationship. All AEs will be followed to adequate resolution.

Any medical condition that is present at the time that the subject is screened should be considered as baseline and not reported as an AE. However, if the severity of any pre-existing medical condition increases at any time during the study, it should be recorded as an AE.

All AEs must be graded for severity and assessed for relationship to study product (see definitions below). Adverse events characterized as intermittent require documentation of onset and duration of each episode. The start and stop date of each reported AE will be recorded on the appropriate data collection form and eCRF.

Severity of Event:

All AEs will be assessed by the site principal investigator or appropriate sub-investigator using the protocol-defined grading system (Section 15.2.2-15.2.3). For events not included in the protocol defined grading system, the following guidelines will be used to quantify severity:

- *Mild (Grade 1):* events require minimal or no treatment and do not interfere with the patient's daily activities.
- *Moderate (Grade 2):* events result in a low level of inconvenience or concern with the therapeutic measures. Moderate events may cause some interference with functioning and daily activities.
- *Severe (Grade 3):* events interrupt a patient's usual daily activity and may require systemic drug therapy or other treatment. Severe events are usually incapacitating.

Relationship to Study Products:

The study clinician's assessment of the relationship of an AE's relationship to study product is part of the documentation process, but it is not a factor in determining what is or is not reported in the study. If there is any doubt as to whether a clinical observation is an AE, the event should be reported. All AEs must have their relationship to study product assessed using the following terms: related or not related. In a clinical trial, the study product must always be suspect. To help assess, the following guidelines are used:

- *Related:* There is a reasonable possibility that the study product caused the adverse event. Reasonable possibility means that there is evidence to suggest a causal relationship between the study product and the adverse event.
- *Not Related:* There is not a reasonable possibility that the administration of the study product caused the event.

15.2.2 Reactogenicity

Reactogenicity events are AEs that are known to occur with Tice® BCG. Reactogenicity events will be analyzed according to the following grading scales:

Table 1: Reactogenicity Events Grading Scales

Local Reaction	Mild (Grade 1)	Moderate (Grade 2)	Severe (Grade 3)
Pain – experienced without touching the injection site	Subject is aware of pain but it does not interfere with daily activity and no pain medication is taken	Subject is aware of pain; there is interference with daily activity or it requires use of pain medication	Subject is aware of pain and it prevents daily activity
Tenderness – hurts only when injection site is touched	The area immediately surrounding the injection site hurts only when touched and it does not	The area immediately surrounding the injection site hurts when touched and it interferes with daily activity	The area immediately surrounding the injection site hurts when touched and it prevents daily activity

	interfere with daily activity		
Erythema/Redness*	Does not interfere with activity	Interferes with activity	Prevents daily activity
Induration/Swelling*	Does not interfere with activity	Interferes with activity	Prevents daily activity
Drainage	Continuous use of bandage cover or less than 2, 2x2 gauze pads/day	Needs 2-4, 2x2 gauze pads/day	Needs more than 4, 2x2 gauze pads/day

* Will be also measured in mm but size will not be used as halting criteria.

Erythema/redness, induration/swelling and lesion as analyzed by measurement will be graded as follows:

Table 2: Erythema/Redness, Induration/Swelling and Lesion Measurement Grading Scales

	Small	Medium	Large
Total Erythema/Redness*	<20 mm	20-50 mm	>50 mm
Maximum Diameter of Induration/Swelling*	<20 mm	20-50 mm	>50 mm
Central Lesion	<10 mm	10-30 mm	>30 mm

* Measurement will not be used as halting criteria

Table 3: Reactogenicity Events Grading Scales (Continued)

Systemic (Subjective)	Mild (Grade 1)	Moderate (Grade 2)	Severe (Grade 3)
Chills	No interference with activity	Some interference with activity	Significant interference, prevents daily activity
Malaise/Fatigue	No interference with activity	Some interference with activity	Significant interference, prevents daily activity
Headache	No interference with activity	Some interference with activity	Significant interference, prevents daily activity
Night Sweats	No interference with activity	Some interference with activity	Significant interference, prevents daily activity
Nausea	No interference with activity	Some interference with activity	Significant interference, prevents daily activity
Vomiting	No interference with activity	Some interference with activity	Significant interference, prevents daily activity
Diarrhea	No interference with activity	Some interference with activity	Significant interference, prevents daily activity
Rhinorrhea	No interference with activity	Some interference with activity	Significant interference, prevents daily activity
Cough	No interference with activity	Some interference with activity	Significant interference, prevents daily activity

Wheezing/Shortness of Breath	No interference with activity	Some interference with activity	Significant interference, prevents daily activity
------------------------------	-------------------------------	---------------------------------	---

Vital signs[#] (oral temperature, pulse and blood pressure) will be analyzed according to the following grading scales:

Table 4: Vital Signs Grading Scales

Systemic (Quantitative)	Mild (Grade 1)	Moderate (Grade 2)	Severe (Grade 3)
Fever*	38.0-38.4°C 100.4-101.1°F	38.5-38.9°C 101.2-102°F	≥39°C ≥102.1°F
Tachycardia - beats per minute [†]	101-115	116-130	>130
Bradycardia - beats per minute	45-49	40-44	<40
Hypertension (systolic) mm Hg	141-150	151-155	>155
Hypertension (diastolic) mm Hg	91-95	96-100	>100
Hypotension (systolic) mm Hg	85-89	80-84	<80
Hypotension (diastolic) mm Hg	45-49	40-44	<40

Vital Signs assessed at Day 1 will be considered as baseline.

* Oral temperature, no recent hot or cold beverages or smoking. Note: A fever can be considered not related to the study product if an alternative etiology can be documented and it is confirmed to be not related to the study product by the Independent Safety Monitor at the site.

† Subject at rest.

15.2.3 Additional Adverse Event Characterization and Severity Grading

Lesions at the ID challenge site will be characterized by the study site staff as follows:

1. Erythematous Macule: flat red spot.
2. Non-Erythematous Papule: a small, circumscribed, non-erythematous, palpable elevation in the skin.
3. Erythematous Papule: a small, circumscribed, erythematous, palpable elevation in the skin.
4. Vesicle: clear fluid filled papule.
5. Pustule: cloudy, purulent fluid filled papule.
6. Ulcer: an open lesion on the surface of the skin caused by superficial loss of tissue, often attended by the formation of pus.
7. Eschar/Crust: a lesion with an erythematous base and a central scab (a coagulation product of blood, serum, pus, or a combination of two or more of these).
8. Healed: previously observed lesion that has dried up without any persistent induration, ulcer, or eschar. Redness under an area of previous eschar formation seen after the eschar

has fallen off during the healing process would not be considered active erythema, but instead would be considered evidence of a healed lesion.

9. Scar: replacement of normal skin with fibrous tissue (other than keloid formation).
10. Keloid: nodular scar.

Severity Grading for Lymphadenopathy

The site principal investigator or appropriate sub-investigator licensed to make medical diagnoses will assess the severity of axillary, cervical, and epitrochlear lymphadenopathy bilaterally by applying the grading scale in the following table:

Table 5: Severity Grading for Lymphadenopathy

Grade	Definition
Grade 0 (none)	No palpable nodes, or all nodes < 1 cm (pea-sized), mobile, and nontender.
Grade 1 (mild)	At least one node \geq 1 cm (pea-sized) but < 2.5 cm (cherry-sized), but mobile and non-tender or tender only with firm pressure.
Grade 2 (moderate)	At least one node \geq 2.5 cm (cherry-sized) or tender to light touch or spontaneously reported as painful, but not causing significant limitation of normal everyday activities.
Grade 3 (severe)	At least one node that is tender to light touch or spontaneously reported as painful AND causing significant limitation of normal everyday activities. Any one of palpable fluctuance or heat, fixation to underlying tissues, or visible erythema.

Severity Grading for Clinical Safety Laboratory Adverse Events

Table 6: Severity Grading for Clinical Safety Laboratory Adverse Events - Hematology

Hematology	Mild (Grade 1)	Moderate (Grade 2)	Severe (Grade 3)
WBC (Increase) 10^3 /UL	10.6 – 15.0	15.1 – 20.0	>20.0
WBC (Decrease) 10^3 /UL	2.5 – 3.9	1.5 – 2.4	<1.5
HgB (Female) g/dL	10.1 – 11.4	8.5 – 10	<8.5
HgB (Male) g/dL	11.0 – 12.4	9.5 – 10.9	<9.5
Platelets (Decrease) 10^3 /UL	125 – 139	100 – 124	<100

Table 7: Severity Grading for Clinical Safety Laboratory Adverse Events - Chemistries

Chemistries	Mild (Grade 1)	Moderate (Grade 2)	Severe (Grade 3)
Creatinine mg/dL	1.31 – 1.70	1.71 – 2.00	>2.00
ALT (SGPT) (Female) IU/L	41 – 100	101 – 200	>200

ALT (SGPT) (Male) IU/L	56 – 138	139 – 275	>275
------------------------	----------	-----------	------

15.2.4 *Serious Adverse Events*

Serious Adverse Event (SAE):

An adverse event or suspected adverse reaction is considered “serious” if, in the view of either the site principal investigator or sponsor, it results in any of the following outcomes:

- Death.
- A life-threatening adverse event*.
- Inpatient hospitalization or prolongation of existing hospitalization.
- A persistent or significant incapacity or substantial disruption of the ability to conduct normal life functions, or
- A congenital anomaly or birth defect.
- Important medical events that may not result in death, be life threatening, or require hospitalization, may be considered serious when, based upon appropriate medical judgment, they may jeopardize the patient or subject and may require medical or surgical intervention to prevent one of the outcomes listed in this definition. Examples of such medical events include allergic bronchospasm requiring intensive treatment in an emergency room or at home, blood dyscrasias or convulsions that do not result in inpatient hospitalization, or the development of drug dependency or drug abuse.

* Life-threatening adverse event. An adverse event is considered “life-threatening” if, in the view of either the investigator or sponsor, its occurrence places the patient or subject at immediate risk of death. It does not include an adverse event that, had it occurred in a more severe form, might have caused death.

All SAEs will be:

- Assessed for severity and relationship to study product and alternate etiology (if not related to study product) by a licensed study physician.
- Recorded on the appropriate SAE form and eCRF.
- Followed through resolution or stabilization by a study clinician licensed to make medical diagnoses.
- Reviewed and evaluated by the SMC periodically. Related and unexpected SAEs will also be reviewed by the IRB.

15.2.5 *Procedures to be Followed in the Event of Abnormal Laboratory Test Values or Abnormal Clinical Findings*

The site principal investigator is responsible for reporting all AEs/SAEs that are observed or reported during the study, regardless of their relationship to study product. AEs/SAEs, abnormal laboratory test values or abnormal clinical findings will be documented, reported and followed appropriately. Adverse events will be assessed through approximately 8 weeks following Tice® BCG administration. Serious adverse events will be assessed for the study duration.

15.3 **Reporting Procedures**

- Document AEs from Visit 02 (Day 0) through Visit 10 (Day 56±2).
- Document SAEs from Visit 02 (Day 0) through Visit 15 (Day 114±1).

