 - Unsolicited AEs/SAEs recorded Days 1-114,
 - Concomitant medications recorded Days 1-114.
- Collection of used dressing/gauze.

Days 4 (clinic visit 6), 5 (clinic visit 7), 6 (clinic visit 8), 8 ± 1 (clinic visit 9), 15 ± 1 (clinic visit 10), and 28 ± 1 (clinic visit 11)

- INH dosing days 4, 5, and 6 only: For the 5 participants assigned to Group 1, they will take INH: oral tablets of either three 100mg tablets (total 300mg) or one 300mg tablet for 3 days post BCG dosing,
- Days 8 ± 1 (clinic visit 9) and 15 ± 1 (clinic visit 10) only: Repeat skin biopsy,
- Assess ID challenge site,
- Review health status and AEs/SAEs that were recorded on the memory aid eCRF device,
- Review concomitant medications,
- Assess for lymphadenopathy if indicated based on review of interim medical history and clinical assessment,

- Targeted physical exam and clinical assessment may be performed if indicated based on review of interim medical history, reactogenicity (as applicable),
- Blood draws via venipuncture for immunogenicity and mycobacteria assays:
 - Day 4: 6.5mls (1.5 tsp),
 - Day 8±1: 74.5mls (5 tablespoons (tbs)),
 - Day 15±1: 56.5mls (4 tbs),
 - Day 28±1: 94.5mls (6 tbs),
- Collect used dressing/gauze,
- Photograph of ID challenge site.

Days 16-114±1

- On-going participant self-evaluations that will be recorded on their memory aid eCRF device for pain, tenderness and drainage. Participants can record their temperature if taken.

Days 56±2 (clinic visit 12) and 84±3 (clinic visit 13)

- Day 56±2 (clinic visit 12) only: Repeat skin biopsy
- Assess ID challenge site (if an abnormal BCG injection site is identified see Abnormal BCG Injection Site Procedures in section 11.3),
- Review health status and AEs/SAEs that were recorded on the memory aid eCRF device,
- Review concomitant medications,
- Assessments for lymphadenopathy if indicated based on review of interim medical history and clinical assessment,
- Targeted general exam and clinical assessment may be performed if indicated based on review of interim medical history, reactogenicity (as applicable),
- Blood draws via venipuncture for immunogenicity and mycobacteria assays:
 - Day 56±2: 94.5mls (6 tbs)
 - Day 84±3: 94.5mls (6 tbs)
- Collect used dressing/gauze,
- Photograph of ID challenge site.

Day 98±1 (clinic visit 14)

- Assess ID challenge site,
- Review health status and AEs/SAEs that were recorded on the memory aid eCRF device,
- Review concomitant medications,

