11.4 Withdrawal Procedures

Participants who discontinue from the study will be asked to complete visits 14-17. Visits 14-17 will occur using the same chronology as in the procedures schedule. If a female becomes pregnant, PBMC will not be collected on visit 17. However, PBMC will be collected from all other participants. If the participant refuses to complete visits 14-17, they will be asked to complete visit 17 which should occur at least 7 days, but \leq 30 days, after the dose of BCG.

Procedures to be performed on visits 14-17: see above in section 11.2 Clinic Visit Schedule.

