13.1 Primary Endpoint

- The rate of AE's/SAE's related to Tice® BCG administration reported at any point during the study,
- Summary of the distribution of viable BCG bacteria from intradermal challenge sites at 4 time points (approximately 3 days and 1, 2, and 4 weeks following Tice® BCG administration), as detected by quantitative CFU plating. The distribution will be summarized in terms of its central tendency (mean or GM) and its precision represented by the appropriate 95% confidence interval.

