15.0 ASSESSMENT OF SAFETY

15.1 Specification of Safety Parameters

Safety will be assessed by the frequency and severity of:

1. Tice® BCG-related serious adverse events occurring throughout the course of the study,
2. Solicited Adverse Events – reactogenicity events following Tice® BCG administration:
 - a) Local reactions including pain, tenderness, erythema/redness, and induration/swelling at the injection site.
 - b) Systemic reactions including fever, chills, malaise/fatigue, headache, night sweats, nausea, vomiting, diarrhea, rhinorrhea, cough, and wheezing or shortness of breath.
3. Lesion characterized as erythematous macule, non-erythematous papule, erythematous papule, vesicle, pustule, ulcer, eschar/crust, healed, scar, or keloid,
4. Lymphadenopathy,
5. Clinical safety laboratory adverse events to include WBC, hemoglobin, and platelet count, creatinine and ALT (SGPT),
6. Unsolicited Adverse Events.
 - a) Non-serious adverse events occurring in the 56 days following Tice® BCG administration.

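### The primary AE rate has two incompatible windows for non-serious events, whole study and about Day 56, and the visit labels in 15.3 do not match the schedule

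*Combined protocol and SAP*

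**What the plan says.** **Whole-study window.** Section 13.1 counts AEs and SAEs "related to Tice® BCG administration reported at any point during the study". Section 15.2.1 requires AEs arising on study to be documented whatever their cause and followed until they resolve. In Section 11.2 the participant diary covers the same span: "Unsolicited AEs/SAEs recorded Days 1-114". Appendix B shows staff review of AEs and SAEs at every visit from Visit 2 to Visit 17.

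**Day 56 window.** Under unsolicited events, Section 15.1 lists "Non-serious adverse events occurring in the 56 days following Tice® BCG administration". Section 15.2.5 says "Adverse events will be assessed through approximately 8 weeks following Tice® BCG administration", followed by "Serious adverse events will be assessed for the study duration". Section 15.3 says "Document AEs from Visit 02 (Day 0) through Visit 10 (Day 56±2" for AEs and "Document SAEs from Visit 02 (Day 0) through Visit 15 (Day 114±1" for SAEs. Yet 15.2.5 opens by making the investigator responsible for reporting every AE and SAE seen or reported in the study.

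**Analysis.** Section 18.1 plans descriptive safety summaries by group and gives no AE window.

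**Early termination.** Section 11.4 first asks participants who discontinue to complete Visits 14-17 on the usual timetable. Of those who refuse, it says "they will be asked to complete visit 17 which should occur at least 7 days" and no more than 30 days after the BCG dose.

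**The concern.** The window decides which events enter the numerator of a primary endpoint. Two analysts could each follow this protocol and report different AE rates. With five participants per group, one participant more or fewer with an event moves a group's proportion by 1/5 = 20 percentage points.

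Continued diary recording does not settle the matter. Section 13.1 counts only BCG-related events, and relatedness is a clinician's judgement made when an AE is documented (15.2.1). If staff follow 15.3 and stop documenting non-serious AEs at Day 56, a later diary entry may have no grade and no causality assessment, and so could not be classified for the endpoint. Late local events are plausible on the protocol's own account: 5.8.1 describes ulcers that take weeks to heal, 11.3 follows abnormal sites until they resolve, and Appendix B records site pain, tenderness and drainage to Day 114.

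**Working it through.** **1. The plan's own figure.** Section 18.1 gives 76% and 37% for at least one and at least two events among five participants at a true rate of 25%.

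- P(≥1) = 1 − 0.75^5 = 1 − 0.2373 = 0.763
- P(≥2) = 1 − 0.2373 − 5 × 0.25 × 0.75^4 = 0.367

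Both reproduce, as does the rest of the table. These probabilities do not depend on the window unless the event rate does.

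**2. Follow-up days outside the Day 56 window.** Follow-up ends at Day 114 (11.2, Visit 17). Share outside = (114 − window end)/114.

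- Nominal Day 56: 58/114 = 50.9%
- Visit held on Day 58, the late edge of ±2: 56/114 = 49.1%
- SAEs, printed end Day 114: 0%

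These are shares of days, not of events.

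**3. What this could mean for detection (assumption).** The documents do not say when events occur. Take a 25% whole-study risk per participant and suppose a share s of it falls inside the window, so that P(≥1 of 5) = 1 − (1 − 0.25s)^5.

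| Share of risk inside window | P(≥1 of 5) |
|---|---|
| 50% | 0.49 |
| 75% | 0.65 |
| 90% | 0.72 |
| 100% | 0.76 |

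With a constant hazard over 114 days, the risk to Day 56 is 1 − 0.75^(56/114) = 0.132 and P(≥1 of 5) = 1 − 0.868^5 = 0.51. That is probably pessimistic, because the documents place expected reactions early (see the objection).

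**4. Visit labels.**

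| Day | 11.2 and Appendix B | 10.6.4, blood draws | 10.6.4, biopsies | 15.3 |
|---|---|---|---|---|
| 15 | Visit 10 | Visit 8 | Visit 10 | – |
| 56 | Visit 12 | Visit 10 | Visit 12 | Visit 10 |
| 100 | Visit 15 | – | – | – |
| 114 | Visit 17 | Visit 15 | – | Visit 15 |

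Section 15.3 agrees with the blood-draw list in 10.6.4. That list goes from Day 4 (Visit 6) straight to Day 8 (Visit 7), whereas 11.2 has Days 5 and 6 as Visits 7 and 8. The two numberings therefore differ by two from Day 8 on, which suggests an older schedule without those two visits. Section 10.6.4 uses both numberings.

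**5. Section 11.4.** A visit no later than 30 days after the BCG dose cannot be held for a participant who leaves after Day 30 and refuses Visits 14-17. Days 31-114 are 84/114 = 74% of follow-up days. This is not a share of participants; no dropout rate is given.

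**The case against.** The best defence is that the shorter window is deliberate. Section 15.2.5 openly ends non-serious AEs before SAEs, and such a design is legitimate. The documents also place expected reactions early: flu-like symptoms last one or two days (5.8.1), and active drainage lasts about six weeks (8.2), which is before Day 56. Collection does not stop: 15.2.1, the diary, the visit reviews and the extra visits in 11.3 all continue. In 15.1 the 56-day limit sits only under unsolicited events, not under local reactions, lesions or lymphadenopathy.

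All of this limits the likely loss. It does not remove the conflict, because 15.2.5 and 15.3 limit AEs generally and 13.1 sets no limit.

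Some stronger readings are tempting but unsupported:

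- **AE capture ends at Day 15.** Visit 10 is Day 15±1 in 11.2, so a reader might infer that 99/114 = 87% of follow-up is lost. But 15.3 prints Day 56±2, 15.1 and 15.2.5 support that day, and 10.6.4 uses the same label. There are two windows and a labelling mismatch, not three windows, and the uncovered share is about half rather than most.
- **SAE capture ends at Day 100, 14 days early.** This too needs the visit label to override the printed Day 114±1, and 15.2.5 carries SAEs through the whole study.
- **Biopsy and PPD events would be lost.** Purely procedural events are not BCG-related and would not enter the 13.1 rate under either window.
- **The AE rate decides whether the model is safe.** No threshold is set; 18.1 relies on description and clinical judgement.

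**Conclusion.** The inconsistency is real and nothing in the protocol resolves it. The primary AE rate has a whole-study window in 13.1, supported by 15.2.1, 11.2 and Appendix B, and a window of about 56 days for non-serious AEs in 15.1, 15.2.5 and 15.3. About half of follow-up days (49-51%) fall between the two. The share of events affected cannot be derived from the documents; the detection figures above are illustrations under stated assumptions. SAEs are unaffected if the printed days govern, and the sample size and the 18.1 table stand. The conflict concerns which events are graded, assessed for causality and counted, not whether they are collected. It should be settled before analysis because it defines the numerator of a primary endpoint. The visit labels are a separate clerical mismatch, and the 11.4 timing is a minor point that affects only participants who refuse Visits 14-17 and leave after Day 30.

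**What to change.** - **Window.** State one window for the primary AE endpoint by day number. Day 0 to Day 114±1 matches 13.1, the diary and the visit reviews; align 15.1, 15.2.5 and 15.3 with it. The cost is revised wording plus some extra grading and causality assessment of non-serious AEs after Day 56.
- **Alternative.** If the shorter period for non-serious AEs is intended, rewrite 13.1 to say so, reconcile 15.2.1 and the opening of 15.2.5, and say how later diary entries are handled. This avoids the extra grading but narrows the endpoint.
- **Visit numbering.** Use one numbering in 10.6.4 and 15.3, consistent with 11.2 and Appendix B. This costs wording only.
- **Section 11.4 (minor).** For participants who refuse Visits 14-17, reconcile the anchor of the Visit 17 timing with the date of discontinuation, so that it can be met after Day 30.
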